### **11.3. Planned Interim Analyses (if applicable)**

No interim analysis for futility or efficacy is proposed because this is a small sample study and the penalty for an early look at the outcome data would compromise the study. However, a safety review will be done periodically.

#### **11.3.1. Safety Review**

Safety reports will be generated and sent to DMID to be disseminated to the DSMB. This report includes hematology and safety laboratory values and adverse events (serious and non-

serious). In addition, Section 9.7 provides a table of halting rules based on the number of subjects experiencing Grade 3 or 4 neutropenia for consideration by the DSMB.

### **11.3.2. Immunogenicity or Efficacy Review**

None.

## **11.4. Final Analysis Plan**

### **11.4.1. Primary Outcome**

Primary analysis will be based on intent-to-treat population. Categories utilized for hearing assessment of each ear for each time point are normal hearing, mild hearing loss, moderate hearing loss, and severe hearing loss. Based on the hearing assessment of each ear at Month 6 and at Baseline, change in each ear will be categorized into binary outcomes: improved + no change versus other (i.e., worsened). For example, normal in the left ear at baseline and moderate in the same ear at Month 6 will be considered as worsened. The primary outcome will be analyzed using logistic regression based on generalized estimating equations (GEE) in order to accommodate the correlation between the left and right ears of a subject in the modeling. In addition, if there are enough data available we will adjust the analyses by whether or not a subject at birth is asymptomatic or symptomatic from their congenital CMV infection. Additional analyses will be performed to adjust for age and site plus any imbalances in the demographic and clinical characteristics to determine if adding them to the model will impact the results. P-values < 0.05 will be considered significant for the primary outcomes.

A single, independent study audiologist who is masked (blinded) to treatment assignment will assess the audiology test battery for each subject and assign the classifications of normal hearing, mild hearing loss, moderate hearing loss, or severe hearing loss based upon their hearing thresholds (in decibels). The classifications will be assigned by ear (one for the left ear and one for the right ear), giving “total ear” classifications. Following this, the study audiologist will assign the “best ear” classification for the subject at that study visit; for example, if a subject had mild hearing loss in their left ear and severe hearing loss in their right ear, then the “best ear” classification will be mild hearing loss.

Primary analyses will be done on the first 54 subjects recruited. If there were subjects enrolled as replacement for dropouts or missing outcome, these added subjects will be included in the secondary analyses.

For those with missing outcome due to missing baseline and/or Month 6 audiology (including dropouts), we will exclude them from the primary analysis. However, we will perform sensitivity analysis by replacing all missing data with “worsening” outcome.”

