## PROTOCOL SUMMARY

Title:	A Phase II Randomized and Controlled Investigation of Six Weeks of Oral Valganciclovir Therapy in Infants and Children with Congenital Cytomegalovirus Infection and Hearing Loss
Phase:	II
Population:	Fifty-four male and female infants/toddlers 1 month through 3 years of age (up to the 4 th birthday) with sensorineural hearing loss and congenital CMV infection. Up to 20% (n=10) over-enrollment is allowed to replace subjects who drop-out or who have inadequate audiology assessments. Subjects will be randomized 1:1 to Investigational drug or placebo.
Number of Sites:	17 (listed in Section 1)
Study Duration:	3.5 years from enrollment of first study subject
Subject Participation Duration:	6 months
Description of Agent or Intervention:	Investigational Drug: Valcyte (valganciclovir hydrochloride) Powder for oral solution: 16.0 mg/kg twice daily  Placebo: Simple Syrup as 60-90% sucrose
Objectives:	Primary: 

• The primary objective is to assess whether a six week course of oral valganciclovir can stabilize the hearing of children with congenital CMV infection who present with hearing loss. This will be accomplished by evaluating changes in hearing in either ear at 6 months from baseline.

 Secondary: 

• To define the following responses as a function of systemic exposure to ganciclovir (active metabolite of valganciclovir):

○ CMV viral load in blood

○ CMV viral load in urine

○ CMV viral load in saliva

• To define the safety and tolerability of valganciclovir in enrolled subjects.

 Tertiary:

- To define the pharmacokinetics of ganciclovir (metabolite) following administration of valganciclovir (prodrug) in enrolled subjects.

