## **4. STUDY DESIGN**

This is a Phase II international, multi-center, double-blind, placebo-controlled evaluation of 6 weeks of valganciclovir treatment for children (up to 4 years of age) with virologically-confirmed congenital CMV infection and hearing loss. Patients who are between 1 month and 4 years of age and who have SNHL are eligible for enrollment on the study. **Enrollment on the study occurs when eligibility is confirmed and the informed consent is signed.** Following the signing of informed consent, the subject's Guthrie card will be retrieved and tested for CMV DNA by PCR unless there is a virologically confirmed diagnosis of congenital CMV infection made within the first 30 days of life. **Randomization on the study occurs when the diagnosis of congenital CMV infection is confirmed,** and the subject then is assigned to either receive 6 weeks of oral valganciclovir or 6 weeks of placebo. Study subjects will be stratified according to age at randomization (1 through 11 months, 12 through 23 months, 24 through 35 months, and  $\geq 36$  months) and CMV involvement (symptomatic and asymptomatic at birth) as a marker of disease severity. The sample size of randomized, evaluable subjects is 54. Dropouts and subjects with audiology assessments that are inadequate for study comparison will be replaced (up to 20%, or  $n=10$ ). Baseline study assessments (see Section 7.2) will be performed following randomization. Subjects will be followed for 6 months post randomization. During the six week treatment period, study subjects will be followed every 2 weeks. Subjects will also be seen at approximately one month following the final dose (Study Day 70), and again at Study Months 4 and 6.

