## **9.6. Halting Rules**

### **9.6.1. Discontinuation of Study participation for individual subject**

Subjects with neutropenia, thrombocytopenia, renal impairment, or hepatotoxicity will be discontinued from study treatment if the criteria outlined in Section 6.3 are met. Since the primary endpoint requires comparison of baseline and 6 month audiology assessments, dropouts and subjects with audiology assessments that are inadequate for study comparison will be replaced in order to reach the target of sample size.

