### **11.2. Sample Size Considerations**

Subjects will be randomized 1:1 to valganciclovir oral solution or valganciclovir placebo. A **sample size of 54 (27 in each arm)** has 90% power to detect a worsening of hearing from 40% to 8.0% in the treatment group based on analyzing two correlated binary outcomes with correlation coefficient of 0.55 at 2.5% level of significance (using PASS 2008 program). Randomization will be stratified by age at randomization (1 through 11 months, 12 through 23 months, 24 through 35 months, and  $\geq 36$  months) and by CMV involvement (symptomatic and asymptomatic at birth) as a marker of disease severity.

Efficacy and safety analysis will be based on intent-to-treat population (ITT), defined as any child who receives at least one dose of study medication and who has complete hearing assessment data at baseline and Month 6. Children who completed the full six weeks of study medication and have hearing assessment data at baseline and Month 6 will be included in a per protocol (PP) analysis of efficacy, which will be performed as a sensitivity analysis. Since the primary endpoint requires comparison of baseline and 6 month audiology assessments, dropouts and subjects with audiology assessments that are inadequate for study comparison will be replaced.

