6.2 Analysis Populations

(ICH E3; 9.7.1, 11.4.2.5. ICH E9; 5.2)

All enrolled subjects will be included in the basic demographic and clinical summaries and analyses. Only subjects who took at least one dose of the blinded treatment and who have completed hearing assessment data at baseline and Month 6 will be included in the analyses of study outcomes that compare treatment groups based on the intention-to-treat (ITT). Safety analyses will be done on all participants enrolled in the study. Children who have completed the full six weeks

of study medication and have hearing assessment data at baseline and Month 6 will be included in a per-protocol (PP) analysis of efficacy, which will be performed as a sensitivity analysis.

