6.4 Missing Data

(ICH E3; 9.7.1, 11.4.2.2. ICH E9;5.3. EMA Guideline on Missing Data in Confirmatory Clinical Trials)

Primary analyses will be done on the first 54 subjects recruited. If there were subjects enrolled as replacement for dropouts or missing outcome, these added subjects will be included in the secondary analyses.

For those with missing outcome due to missing baseline and/or Month 6 audiology (including dropouts), we will exclude them from the primary analysis. However, we will perform sensitivity analysis by replacing all missing data with “worsening” outcome.

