For those with missing outcome due to missing baseline and/or Month 6 audiology (including dropouts), we will exclude them from the primary analysis. However, we will perform sensitivity analysis by replacing all missing data with “worsening” outcome.

For those study subjects proceeding to cochlear implantation during the course of the study, he/she will not require additional study-related hearing assessments following the implantation procedure. Efficacy analyses will utilize “severe” as final hearing assessment at Month 6 for those who underwent cochlear implantation.

The summary statistics will be produced in accordance with section 7.

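### Replacement children are barred from the primary analysis, so every child without evaluable audiology among the first 54 takes the primary test below the 54 on which the 90% power rests.

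*Protocol*

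**What the plan says.** **Design.** Protocol section 4 states: "The sample size of randomized, evaluable subjects is 54". The Protocol Summary says that "over-enrollment is allowed to replace subjects who drop-out or who have inadequate audiology assessments", with a limit of 10. Protocol 9.6.1 gives the purpose: such children "will be replaced in order to reach the target of sample size". Protocol 5.4.6 and 11.2 justify replacement by the primary endpoint's need for audiology at baseline and Month 6.

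**Analysis.** Protocol 11.4.1 states: "Primary analyses will be done on the first 54 subjects recruited". SAP 6.4 and 8.1 repeat the rule. On replacements, SAP 6.4 says "these added subjects will be included in the secondary analyses". For children with missing baseline or Month 6 audiology, SAP 8.1 says "we will exclude them from the primary analysis". Scoring missing outcomes as worsened is a sensitivity analysis only.

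**Population label.** Protocol 11.2 defines ITT as a child with at least one dose "who has complete hearing assessment data at baseline and Month 6". SAP 6.2 likewise limits it to dosed children "who have completed hearing assessment data at baseline and Month 6 will be included in the analyses of study outcomes".

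**The concern.** The design and analysis sections define different primary populations. Replacement exists so that 54 evaluable children are available for the primary endpoint, yet the analysis rule keeps every replacement out of that endpoint's test. There is no other margin for loss in the 54.

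Two things are at stake. The primary test may be smaller than the power statement assumes. And replacement infants and toddlers would be randomized, dosed and bled without contributing to the comparison that justified replacing anyone.

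Separately, a set that requires complete outcome data is labelled ITT. Readers would credit it with a protection against post-randomization exclusion that it does not have.

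**Working it through.** **1. What the 54 means.** Protocol 7.1 says that children enrolled but not randomized do not count toward the sample size, so the natural reading is the first 54 randomized. It cannot mean the first 54 evaluable: replacements would then be among the 54, and the next sentence puts them in the secondary analyses. No section admits a replacement to the primary test.

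**2. Inputs** (Protocol 11.2 and SAP section 5): 27 per arm, worsening 40% versus 8%, between-ear correlation 0.55, 2.5% level, 90% power. Sidedness is not stated.

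**3. Formula.** With two ears per child, effective ears per arm are n_eff = 2n/(1 + 0.55). Power is that of a pooled-variance z test:

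Φ{[0.32 − 1.96·√(p̄(1−p̄)(1/n₁+1/n₂))] / √(0.40·0.60/n₁ + 0.08·0.92/n₂)}

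Here n₁ and n₂ are the effective ears in the two arms and p̄ is the pooled rate (0.24 when the arms are equal).

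**4. The plan's own figure.** At 27 per arm, n_eff = 54/1.55 = 34.84. The null standard error is 0.1023 and the alternative 0.0949. So (0.32 − 1.96 × 0.1023)/0.0949 ≈ 1.26, and power is 89.6%, which matches 90%. This reads 2.5% as one-sided, in line with the two-sided p < 0.05 rule in Protocol 11.4.1. Two-sided 2.5% gives 83.0% with the same formula. A simulated cluster-robust logistic test (GEE type) at two-sided 5% gives 0.90.

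**5. Power under the written rule, loss split evenly**

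| Lost from first 54 | Evaluable in primary test | Power |
|---|---|---|
| 0 | 54 | 89.6% |
| 1 | 53 | 89.0% |
| 2 | 52 | 88.4% |
| 4 | 50 | 87.1% |
| 6 | 48 | 85.7% |
| 8 | 46 | 84.1% |
| 10 | 44 | 82.4% |

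If all 10 losses fall in one arm, power is 82.1% (placebo, 17 versus 27) or 78.9% (valganciclovir, 27 versus 17).

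**6. The part due to the rule.** Suppose 10 are lost and 10 replacements are admitted, with the same loss rate of 10/54. Evaluable children are 44 + 10 × (1 − 10/54) = 52.1, and power is 88.5%. The rule costs 88.5 − 82.4 = 6.1 points. Randomized children number 54 + 10 = 64, of whom 44 are in the primary test.

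**The case against.** The strongest reply is that the effect is modest and its exact size uncertain.

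- **Size.** With no loss there is no effect. Four losses cost 2.5 points, and balanced loss of 10 still leaves more than 80%. The 78.9% figure needs all 10 losses in one arm. Protocol 11.1 calls this a proof-of-principle study. All of this stands, and it limits the size of the problem.
- **Inputs.** Protocol 2.2 says that 40% versus 5% was used for the power calculation, whereas 11.2 and SAP section 5 say 8%. With 5% the same formula gives 95.5% at 54 and 90.6% at 44. An unpooled test (40% versus 8%) gives 92.1% at 54, 90.1% at 50 and 86.1% at 44. These variants match the stated 90% less well than 89.6% does, and 11.2 is the formal sample-size text. The absolute levels do depend on these choices, and the 5%/8% conflict should be resolved. Under each variant, power falls with each loss.
- **What counts as lost.** Children who stop drug but have both assessments stay in the set. SAP 8.1 scores implanted children as severe at Month 6, although SAP 7.2 leaves out post-implant outcomes. The Month 6 hearing window is wide and clinical audiograms are accepted. These provisions make loss less likely but do not change the rule.
- **Other uses.** Replacements do serve the secondary and safety analyses. The point concerns the primary test only.

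Protocol 5.4.6 and 7.6 say that all randomized children will be in the final analysis. That conflicts with the exclusion rule but does not override the specific wording of 11.4.1.

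**Conclusion.** The concern holds. As written, the number in the primary test is 54 minus those without a dose or without evaluable audiology at both times, and replacements cannot make up the difference. The stated power applies only with zero loss. Over an assumed range of 0 to 10 balanced losses it runs from 89.6% to 82.4%, and about 6 of those 7 points at the ceiling come from the rule itself.

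These figures assume 40% versus 8%, correlation 0.55, a one-sided 2.5% level and a pooled test. The inconsistency between design and analysis does not depend on them. The missing-as-worsened analysis and the dropout comparison in Protocol 5.4.6 help in judging bias but do not restore the primary sample. The primary population should be unambiguous before unmasking.

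**What to change.** - In Protocol 11.4.1 and SAP 6.4 and 8.1, delete the restriction to the first 54 and the sentence assigning replacements to the secondary analyses.
- Define the primary set as all randomized children, replacements included, who took at least one dose and have evaluable baseline and Month 6 audiology, analysed as randomized. State that dosed children without evaluable audiology are left out.
- In Protocol 11.2 and SAP 6.2, call this set complete-case, not ITT. Reconcile Protocol 5.4.6 and 7.6 with it.
- Keep missing-as-worsened as the sensitivity analysis, applied to all randomized and dosed children.
- If the first-54 limit is kept, restate power as 89.6% only with no loss and about 82% at 44 evaluable, with the formula and sidedness given.
- Separate minor point: align the safety population in Protocol 11.2 and SAP 6.2 with the at-least-one-dose set already used in SAP section 9.

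The cost is protocol and SAP wording. The replacement children are already planned, and no new visits or data are needed. Admitting them recovers sample size; it does not remove bias from missing outcomes.

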### **11.4.2. Secondary and Tertiary Outcomes**

Logistic analyses will be utilized to determine if there is treatment effect based on the best ear outcome. As in the total ear analysis, change in the best ear will be categorized into binary outcomes – namely: 1) improved + no change versus others, which examines positive hearing outcomes defined as improved hearing or protection from hearing impairment in subjects who started with normal hearing at baseline; 2) worsened versus others, which examines deterioration or worsening of hearing; 3) improved versus others; and 4) worse + no change versus others. Similar analyses will be performed for total ears (worsened versus others, improved versus others, and worse + no change versus others).

For other secondary and tertiary outcomes, Fisher's exact test will be used to compare binary outcomes (such as detection of viremia or subject with at least one AE or SAE), and Wilcoxon Rank test will be used to compare continuous outcomes (such as quantitative log reduction) between the two treatment groups 6 weeks and 6 months after initial treatment.

Logistic model utilizing generalized estimating equations will also be used to determine the association between change in hearing and change in viral load. Change in viral load over time will be measured by the area under the curve computed using the trapezoidal rule. Spearman rank correlation will be utilized to examine the association between viral load and PK parameters. Poisson regression model will be used to compare the number of AEs/SAEs experienced by subjects between the two groups.

As in the primary outcomes, missing change in hearing outcomes will be replaced by worsened outcome as sensitivity analyses for all secondary hearing outcomes..

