**Description of Study Design:**

This is an international, multi-center, double-blind, placebo-controlled evaluation of 6 weeks of valganciclovir treatment for children (up to 4 years of age) with virologically-confirmed congenital CMV infection and hearing loss. Patients who are between 1 month and 4 years of age and who have SNHL are eligible for enrollment on the study. **Enrollment on the study occurs when eligibility is confirmed and the informed consent is signed.** Following the signing of informed consent, the subject's Guthrie card will be retrieved and tested for CMV DNA by PCR unless there is a virologically confirmed diagnosis of congenital CMV infection made within the first 30 days of life. **Randomization on the study occurs when the diagnosis of congenital CMV infection is confirmed,** and the subject then is assigned to either receive 6 weeks of oral valganciclovir or 6 weeks of placebo. Study subjects will be stratified according to age at randomization (1 through 11 months, 12 through 23 months, 24 through 35 months, and  $\geq$  36 months) and CMV involvement (symptomatic and asymptomatic at birth) as a marker of disease severity. The sample size of randomized, evaluable subjects is 54. Dropouts and subjects with audiology assessments that are inadequate for study comparison will be replaced (up to 20%, or n=10). Baseline study assessments (see Section 7.2) will be performed following randomization. Subjects will be followed for 6 months post randomization. During the six week treatment period, study subjects will be followed every 2 weeks. Subjects will also be seen at approximately one month following the final dose (Study Day 70), and again at Study Months 4 and 6.

At each of the visits during the treatment phase (Study Days 1, 14, 28, and 42), safety labs will be assessed; viral load

[figure not shown]

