## **3. OBJECTIVES**

### **3.1. Study Objectives**

Primary:

- The primary objective is to assess whether a six week course of oral valganciclovir can stabilize the hearing of children with congenital CMV infection who present with hearing loss. This will be accomplished by evaluating changes in hearing in either ear at 6 months from baseline.

Secondary:

- To define the following responses as a function of systemic exposure to ganciclovir (active metabolite of valganciclovir):
  - CMV viral load in blood
  - CMV viral load in urine
  - CMV viral load in saliva
- To define the safety and tolerability of valganciclovir in enrolled subjects.

Tertiary:

- To define the pharmacokinetics of ganciclovir (metabolite) following administration of valganciclovir (prodrug) in enrolled subjects.

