3.3 Derived variables

The primary efficacy assessment will be change in total ear hearing assessment between baseline and 6 months post enrollment. Categories used for hearing assessment of each ear for each time point will be normal hearing, mild hearing loss, moderate hearing loss, and severe hearing loss. Baseline and 6 month hearing categories will be compared and the change in each ear will be categorized into binary outcomes: Improved or no change versus Other (i.e., worsened) Note that the total ear assessment at each time point will be provided by the Independent Audiologist and entered in the database following the rules below and the information provided by the audiology reports.

In the model-based analyses, the “no change” category will be broken down into “Protected: normal to normal” as one category and “No Change: same degree of hearing loss at Baseline and Study Month 6” as another category. The rationale behind this is that if one is interested in the improvement of hearing loss, a subject that has normal hearing at baseline cannot improve further. Hence from an efficacy analysis point of view, the “Protected: normal to normal” can be viewed as protective effect of the drug from hearing deterioration. This analysis approach will be similar to the analysis of the previous CASG study that established the efficacy of 6 weeks of IV GCV in symptomatic congenital CMV disease with CNS involvement.

Analysis of actual viral load will be done using log base 10 transformation. Undetectable viral load value will be replaced by a value of 10. A summary measure of the viral load over time will be calculated two ways. The first approach considers all time points available by calculating the average area under the curve (AUC) (trapezoidal rule) applied to the log base 10 viral load. Average is based on the maximum period of time with viral load data for a given subject. To illustrate, if the calculated AUC for log₁₀ VL for a given subject is 200 from baseline to Day 70, then average AUC is $200/70=2.86$. Taking average AUC will enable us to use and compare data from subjects who did not have viral load values at the later time due to dropping out early, for example, with subjects with complete viral load data. The second approach is to take using difference between Month 6 and baseline log₁₀ VL. The last visit with available VL will be used for those without Month 6 VL. Section 11 contains more details on Viral Load analyses.

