| Table 24c: Summary of Modeling Results (Urine) | 24b | At least one dose of study drug | Quantitative Viral Load (Saliva) | Baseline-Month6 | Therapy Group, Visit | p-value | General linear mixed model with random intercept was fitted for each parameter. Each model contains therapy, time and therapy by time interaction. |
| Table 25: Spearman Rank Correlation between GCV concentration and log10 VL | 24c | At least one dose of study drug | Quantitative Viral Load (Urine) | Day 14, 28, 42 | NA | Correlation, p-value | Spearman Rank Correlation |
| Table 26a: Summary Statistics: Baseline Log10 VL by Change in Total Ear Hearing | 25 | At least one dose of study drug | concentration and log10 VL | Baseline | Baseline Viral Load, Therapy Group | N, Mean, SD, 10th pctl, 90th pctl | NA |
| Table 26b: Association between Baseline Log10 VL and Change (Binary) in Total Ear Hearing | 26a | At least one dose of study drug | VL by Change in Total Ear Hearing | Baseline | Baseline Viral Load, Therapy Group | N, Mean, SD, 10th pctl, 90th pctl with p-values | Generalized linear model for binary outcome using generalized estimating equations with VL as main predictor for unadjusted model; adjusted model includes therapy group |

| | | | | | | | |
|--|-----|---------------------------------|--|-----------------|---|---|--|
| Table 27a: Summary Statistics: Baseline Log10 VL by Change in Best Ear Hearing | 26b | At least one dose of study drug | VL and Change (Binary) | Baseline | Baseline Viral Load, Therapy Group | N, Mean, SD, 10th pctl, 90th pctl | NA |
| Table 27b: Association between Baseline Log10 VL and Change (Binary) in Best Ear Hearing | 27a | At least one dose of study drug | VL by Change in Best Ear Hearing | Baseline | Baseline Viral Load, Therapy Group | N, Mean, SD, 10th pctl, 90th pctl with p-values | Generalized linear model for binary outcome using generalized estimating equations with VL as main predictor for unadjusted model; adjusted model includes therapy group |
| Table 28a: Summary Statistics: Average AUC Log10 VL and Change in Total Ear Hearing | 27b | At least one dose of study drug | VL and Change (Binary) | Baseline-Month6 | AUC Viral Load, Therapy Group | N, Mean, SD, 10th pctl, 90th pctl | NA |

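### The planned exposure-response analysis correlates ganciclovir with on-treatment viral load and leaves out the Day 1 viral load, a covariate the trial already collects and that would be worth adding

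*Protocol*

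**What the plan says.** The secondary objective in Protocol 3.1 reads "To define the following responses as a function of systemic exposure to ganciclovir", and it lists blood, urine and saliva viral load. Protocol 11.4.2 names one method for it, repeated word for word in SAP 8.2: "Spearman rank correlation will be utilized to examine the association between viral load and PK parameters".

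SAP section 17 turns this into "Table 25: Spearman Rank Correlation between GCV concentration and log10 VL". The time-point, covariate, statistic and method cells of that row read "Day 14, 28, 42 | NA | Correlation, p-value | Spearman Rank Correlation". The number and endpoint cells around this row appear displaced by one line, but the title, time points and method agree with each other. The response is therefore the viral load level on treatment, and no baseline term is named.

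Day 1 viral load is available. The design section schedules viral load specimens from all three fluids on Days 1, 14, 28 and 42. The SAP uses baseline-referenced viral load for other questions:

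- Log reduction is compared between arms (Protocol 11.4.2, SAP 8.2).
- In SAP 3.3, "The second approach is to take using difference between Month 6 and baseline log₁₀ VL". That difference is related to hearing in Tables 30 and 31, not to exposure.
- The average AUC in SAP 3.3 and section 11 is a time-averaged log10 level that includes baseline. It is assigned to the hearing association and would not remove baseline differences.

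**The concern.** A response to drug is where a child ends up relative to where that child began. A correlation with the on-treatment level mixes the two. Entry viral load may vary widely: ages run from 1 month to the fourth birthday, and SAP section 15 records that the criterion requiring CMV shedding in urine was removed in Version 4.0. Any part of the on-treatment level that is inherited from Day 1 acts as noise in the exposure correlation.

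There is a second route to error. Protocol 2.1.2.1 reports that bioavailability and renal clearance change in early infancy, so exposure may depend on age. If Day 1 load does too, exposure and Day 1 load become linked, and the unadjusted correlation picks up that link along with any drug effect.

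What is at stake is the reading of the virologic results. Protocol 2.2 expects the viral load data to inform a later study even if the hearing endpoint is not met.

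**Working it through.** The plan gives no power or effect size for this analysis, so there is no stated figure to reproduce.

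**Inputs from the documents:** 27 children in the active arm (Protocol 11.2), before any missing specimens; level of log10 viral load as response; no covariate; undetectable load set to 10, that is log10 = 1 (SAP 3.3).

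**Inputs that are assumptions:** baseline SD of log10 viral load (s_b) 1.0; residual SD (s_r) 0.5 to 0.8; slope 0.35 log10 per SD of exposure; carry-over c from Day 1 to the on-treatment level, varied from 1 to 0; correlation r between exposure and Day 1 load, 0 or ±0.3; exposure measured without error and no detection floor, unless stated.

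**Model:** log10 VL on treatment = c·s_b·B − 0.35·E + s_r·noise, with B and E standardised. Unadjusted Spearman (n − 2 df) is compared with first-order partial Spearman given Day 1 load (n − 3 df), two-sided 5%, 20,000 simulated trials per setting.

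**Why carry-over matters.** With r = 0, the size of the underlying correlation is

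- unadjusted: 0.35 / √(0.35² + c²s_b² + s_r²)
- adjusted: 0.35 / √(0.35² + s_r²)

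At c = 1 and s_r = 0.5 these are 0.35/√1.3725 = 0.30 and 0.35/√0.3725 = 0.57. At c = 0 the two are equal.

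**Power with no exposure-baseline link (s_r 0.5 to 0.8):**

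| Carry-over | Unadjusted | Adjusted for Day 1 |
|---|---|---|
| 1 | 30-24% | 77-45% |
| 0.5 | 60-40% | 82-48% |
| 0.3 | 76-45% | 84-48% |
| 0 | 86-51% | 84-49% |

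**Imperfect exposure.** With reliability 0.3 for a single concentration and c = 1, power is 12-11% unadjusted and 28-16% adjusted.

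**False positives: no drug effect, r = 0.3, s_r = 0.6.** The spurious correlation is r·c·s_b / √(c²s_b² + s_r²). At c = 1 it is 0.3/√1.36 = 0.26; at 0.5, 0.15/√0.61 = 0.19; at 0.3, 0.09/√0.45 = 0.13. The unadjusted test is significant in 24%, 15% and 10% of trials; the adjusted test in about 5%. With r = 0 and no effect, the unadjusted test also keeps about 5%.

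**True effect with a link (c = 1, s_r = 0.6).** The covariance of exposure and level is r·c·s_b − 0.35.

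- r = +0.3 (higher exposure in children with higher Day 1 load): 0.30 − 0.35 = −0.05, nearly cancelled. Power is 6% unadjusted, 58% adjusted.
- r = −0.3: −0.30 − 0.35 = −0.65. The unadjusted test rejects in 72%, partly through confounding, against 63% adjusted.

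**The case against.** The strongest case against has four parts.

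**The size rests on assumptions.** The documents give no spread of Day 1 load and no correlation between Day 1 and on-treatment load. The most relevant figures are the group values in Protocol 2.2 for an earlier study in neonates and young infants: whole blood load fell from about 3.5 logs to under 2 logs over six weeks. That says nothing about carry-over within a child. A reader might infer that the Day 42 level mainly reflects where the child started. The documents do not support that, and at low carry-over the gain from adjustment is small or nil. This part stands.

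**Exposure is poorly measured.** Table 25 uses a single concentration per visit, and each child's three draws fall in different post-dose windows (Protocol 8.2.2.2). A reader might infer that adjustment brings power to near 80%. With reliability 0.3 it does not reach 30%. This part stands as well.

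**There is a detection floor.** Children undetectable on Day 1 cannot show a response, and tied ranks weaken both tests. With about half the children at the floor on treatment and carry-over 1, adjusted power falls to 56-34%. Adjustment does not cure this.

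**The link between exposure and Day 1 load is unproven.** Dosing is per kilogram, and neither the existence nor the sign of a link is given. Confounding by age need not be fully removed by conditioning on Day 1 load alone.

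It is also fair that no listed endpoint is an exposure-viral load association and that an unadjusted Spearman at this sample size is a conventional descriptive choice. None of this restores a baseline term to the analysis or gives a reason to leave it out.

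**Conclusion.** The omission is plain in Protocol 11.4.2, SAP 8.2 and Table 25, and no other section supplies a baseline term for this analysis. In the settings tabulated above, with no exposure-baseline link, adjustment raised power whenever Day 1 load predicted the on-treatment level, and it cost about 2 points when it did not. It held the error rate near 5% where an assumed exposure-baseline link took the unadjusted test to 10-24%.

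How much this matters in the trial cannot be read from the documents. It depends on baseline and residual SD, slope, carry-over, reliability of a single concentration and the fraction at the floor, all of them assumed here.

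Two stronger readings should be resisted. One is that the planned test will produce a false association: that needs both carry-over and an exposure-baseline link, and without the link the test keeps its level. The other is that the trial's conclusions are at risk: the analysis is secondary and unpowered, has no decision rule, and leaves the hearing result untouched. This is a change to consider.

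**What to change.** In Protocol 11.4.2, SAP 8.2 and Table 25, specify a partial Spearman correlation, or a linear regression of log10 viral load at the visit on exposure, in active-arm children, adjusted for the same child's Day 1 log10 viral load in the same fluid. Keep the unadjusted correlation as descriptive.

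Adjustment is preferable to correlating exposure with plain change from Day 1. In a separate simulation with carry-over 0.7, no drug effect and an exposure-baseline correlation of −0.3 to −0.5, the change score gave 7-38% false positives, while the partial correlation stayed at about 4-6%.

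The cost is SAP wording, one covariate already in the database, one degree of freedom, and about 2 points of power if Day 1 load proves uninformative. The report should still state the limits that adjustment does not remove: the detection floor, error in a single concentration, and confounding by age beyond Day 1 load.
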